The outcomes will be assessed during the course of the inpatient admission through chart review. The timing of misoprostol placement will be accurately recorded by the nursing staff. Admission, fetal heart

rate tracing review, and delivery times will be recorded by the nursing staff. Adverse outcomes and maternal/fetal complications rates will be recorded prior to hospital discharge by chart review. Given that all outcomes will be evaluated at the time of inpatient admission, there will be no anticipated loss to follow-up.

Randomization

Randomization will occur according to a predetermined computer-generated stratified randomization scheme prepared by a study statistician. This method will be used to achieve balance among the intervention and control groups in terms of patients' characteristics including BMI >= 40 kg/m², parity, and intent to proceed with mechanical dilation at initiation of misoprostol placement. These three variables will be dichotomous such that there will exist a pre-stratified BMI >=40 kg/m² group, BMI <40 kg/m² group, multiparous group, nulliparous group, proceeding with mechanical dilation, and not proceeding with mechanical dilation. A separate block will be generated for each combination of covariates, and patients will be assigned to the appropriate block of covariates. When subjects have been identified and assigned into blocks, simple randomization will be performed within each block to assign subjects to one of the groups (control versus intervention).

Statistical Analysis

Descriptive statistics will characterize the group of individuals recruited to assess comparability of the treatment and control groups. Chi-Square test or Fisher's exact test will be used for categorical variables. Continuous variables will be examined for normality using the Shapiro-Wilk test; normally distributed continuous variables will be compared using the Student's t-test and those non-normally distributed will be compared using the Mann-Whitney U test. Analysis of the primary outcome will consist of a simple comparison of time from labor induction to delivery between the treatment and control group using generalized linear models. Stratified analyses will be used to identify potentially confounding effects. All tests will be two-tailed and use a significant level of <0.05. Data will be analyzed with the intention-to-treat principle.

[figure not shown]
Blinding

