This study will be double blinded with the research participants and providers/nursing masked to the interventions. A study statistician will create a randomization scheme as described above which will be utilized by the research pharmacy to distribute pre-packaged masked intervention packets.

Power Analysis

Sample size estimations were conducted using G*Power. Our analyses estimated a medium effect based on a 3-hour difference (SD=6) between our treatment (M=15 hours) and control (M=18 hours) groups⁴. These estimations were derived from the work of Carbone et al, Obstet Gynecol. 2013. We computed the required sample size to detect a medium effect with the specified parameters: strata = 8, power = 0.85, α =.05, f=0.25. This yielded a total sample size of approximately 180 participants total, 90 per group. Figure 1 depicts the relationship between sample size and effect size the study proposed. As effect size decreases, sample size increases.

Figure 1. Relationship between effect size and sample size for MD 30 RCT.

Future Plans

If our results demonstrate that 50mcg of vaginal misoprostol provides shorter interval time to delivery, is safe and well-tolerated, and has similar vaginal delivery rates compared to current induction methods, we will plan to seek funding for a multi-center trial to alter current induction methods for obese patients. This will provide a larger and thus more generalizable patient population to provide guideline recommendation changes.

Budget

To achieve a double-blind study, misoprostol doses will be provided as pre-quartered tablets of either 100 mcg tabs (to achieve 25 mcg) or 200 mcg tabs (50 mcg). These tablets are virtually indistinguishable in size. Ascension Hospital Research Pharmacy has provided significantly discounted rates to provide prepackaged blinded doses of misoprostol to this study. Their estimates include:

- Start-up fees \$1125
- Quarterly Maintenance \$100/month 100% = Agreed to discount for Fellow research project
- Combined Enrollment/Dispensing Fees \$150/subject 50% = \$75 x 180 subjects = \$13,500
- Misoprostol tablets 100mcg x 180 subjects = \$100
- Misoprostol tablets 200mcg x 180 subjects = \$100
- Close-out fees \$200
- Total Estimated Research Pharmacy Fees: \$15,025
- Document Translation Fees: \$500
- Standard medical grade weight scale: \$150 (approximate)
- Participant compensation: \$10 x 180 subjects = \$1800

Projected Total Costs: \$17,475

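### Stratification is meant to balance the arms, but simple randomization within strata adds no balance; use permuted blocks and put the three factors in the primary model

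*Combined protocol and SAP*

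**What the plan says.** The Randomization section gives the purpose of stratifying: "This method will be used to achieve balance among the intervention and control groups". The factors are BMI (40 kg/m² or more, or below), "parity, and intent to proceed with mechanical dilation at initiation of misoprostol placement". All three are dichotomous, so there are 2 × 2 × 2 = 8 strata.

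The section uses the word block for a stratum: "A separate block will be generated for each combination of covariates". Within each of these, "simple randomization will be performed within each block to assign subjects to one of the groups (control versus intervention". No block size, minimization or other restriction appears anywhere. The second Blinding section only refers back ("A study statistician will create a randomization scheme as described above"), and the Randomization Procedure says only that REDCap randomizes the patient.

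The Statistical Analysis section says: "Analysis of the primary outcome will consist of a simple comparison of time from labor induction to delivery between the treatment and control group". The method is generalized linear models, with no covariates named. The strata appear in two other places: "Stratified analyses will be used to identify potentially confounding effects" in the same section, and "strata = 8, power = 0.85" in the Power Analysis.

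**The concern.** Stratification balances the arms only when assignment within each stratum is restricted, for example by permuted blocks. With simple randomization, each woman's assignment is an independent coin toss whatever her stratum, so the joint distribution of assignments is the same as with no strata. The stratification has no effect on balance.

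The benefit could still be recovered in the analysis by adjusting for the three factors, but the primary model as described does not contain them. The trial therefore selects three factors as important, collects them before allocation, and uses them neither to balance the arms nor to sharpen the primary estimate. A reader of the trial report would be told that the design secured a balance it did not secure.

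**Working it through.** **Inputs from the document.** Total N = 180, 90 per group; difference 3 h (15 against 18 h); SD 6 h; two-sided alpha 0.05; planned power 0.85; 8 strata; f = 0.25.

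**Assumptions (not in the document).** 30-60% nulliparous, 50% with intended mechanical dilation, 30% with BMI of 40 or more, factors independent. Nulliparity adds d = 0 to 5 h; total SD stays at 6 h.

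**1. The plan's own figure.** Standardized difference = 3/6 = 0.5, so f = 0.5/2 = 0.25, as stated. A two-arm test with one degree of freedom needs 146 women for 85% power, not 180. A noncentral F calculation with 8 groups gives 178 if the numerator degrees of freedom are set to 2, a value the document does not state. At 180 the power is 91.6%. The stated size is therefore on the generous side, and this discrepancy does not affect the present point.

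**2. Balance under the scheme as written.** For a factor of prevalence p, the between-arm difference in prevalence has SD of about √(4p(1−p)/180).

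| p | SD (points) | P(difference ≥ 10 points), normal approximation |
|---|---|---|
| 0.5 | 7.5 | 18% |
| 0.3 | 6.8 | 14% |

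For at least one of three factors with p = 0.5, 0.5 and 0.3: 1 − 0.82 × 0.82 × 0.86 = 42%. Simulation of the written scheme (10,000 trials per setting) gives 15-18% for nulliparity and 40-43% for any of the three.

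A separate simulation with eight equal strata compared three schemes directly:

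| Scheme | P(≥ 10 points on any factor) | Mean arm-size difference | SD of factor difference |
|---|---|---|---|
| No strata | 45% | 10.7 | 7.5 points |
| Strata, simple randomization within | 46% | 10.6 | 7.5 points |
| Strata, permuted blocks of 4 | 0% | 2.0 | 1.4 points |

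The first two rows agree to within simulation error, as theory requires. Blocks of 4 and 6 also give about 0%.

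**3. Validity and power of the written scheme.** Simulated type I error is 4.8-5.2% and power for 3 h is 91-92%. A split of 100:80 or worse has probability 16%, but costs little: power is 91.6% at 90:90 and 91.2% at 80:100.

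**4. What adjustment gains.** The unadjusted SE is 6√(2/90) = 0.894 h. Adjusting for parity removes d²p(1−p) from the variance of 36, so SE = √(36 − d²p(1−p)) × √(2/90), and the equivalent unadjusted N is 180 × 36/(36 − d²p(1−p)).

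| d, p | Remaining variance | SE (h) | Equivalent N |
|---|---|---|---|
| 2 h, 0.5 | 35 | 0.882 | 185 |
| 5 h, 0.5 | 29.75 | 0.813 | 218 |
| 5 h, 0.3 | 30.75 | 0.827 | 211 |

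**5. Why the list and the model must change together.** Blocking removes the between-stratum part of the real variation in the estimate, but an unadjusted test still counts it in the SE. At d = 5, p = 0.5 the effective critical value is about 1.96 × 0.894/0.813 = 2.16, which is a true two-sided level of about 3.1%. Simulation agrees:

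| List and model | Type I error | Power, d = 2 h | Power, d = 5 h |
|---|---|---|---|
| Simple, unadjusted (as written) | 4.8-5.2% | 91-92% | 91-92% |
| Blocks, unadjusted | 4.8% (2 h); 3.0-3.5% (5 h) | – | – |
| Blocks, adjusted | 4.9-5.2% | 92% | 95-96% |
| Simple, adjusted | – | 92% | 94-95% |

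A dash marks a result not tabulated for that combination. Adjustment supplies most of the precision; blocking supplies the balance.

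**The case against.** The strongest reply is that very little is at risk. The unadjusted test is valid, power exceeds the planned 85%, and chance imbalance is already reflected in the SE. A 10-point difference in nulliparity with a 2 h effect moves the estimate by 0.10 × 2 = 0.2 h, against an SE of 0.89 h and a target of 3 h. At that effect size adjustment is worth about five women. The larger gains need an assumed 5 h effect of parity, and the simulation gives an effect to parity only. All of this stands, and it is why the point is not rated higher.

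The second reply is that the wording may be loose. A list prepared in advance by a statistician, one per covariate combination, with 90 per group planned, is compatible with a restricted list. A generalized linear model can also carry covariates, and the eight strata in the power statement suggest that one was in mind. The documents cannot settle this. It does not remove the point, however. If the list is restricted, the text misdescribes it, and the need to name the factors in the model becomes stronger, because the unadjusted test is then conservative.

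A third reply is that simple randomization is the least predictable method. That is true, but varying concealed block sizes and masked envelopes keep the loss small.

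**Conclusion.** The concern holds and should be fixed. As written, the scheme does not have the balancing property claimed for it, and the primary analysis names no factors that would compensate. The chance of a difference of 10 points or more on at least one factor is about 40-43% under the assumed prevalences (46% with equal strata), against about 0% with permuted blocks. The 10-point threshold is a convention chosen for illustration.

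This is not a threat to validity: allocation is unbiased, type I error is about 5%, and power for 3 h is 91-92%. The precision given up ranges from negligible (SE 0.89 against 0.88 h if parity is worth 2 h) to moderate (0.81-0.83 h if it is worth 5 h). The conclusion that simple randomization within strata adds no balance needs none of these assumptions; only the size of the consequences does.

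**What to change.** 1. In the Randomization section, replace the simple-randomization sentence with: *Within each of the 8 strata, participants will be assigned 1:1 using computer-generated permuted blocks of randomly varying size (e.g. 4 and 6), with block sizes concealed from site staff.* If the actual list is already restricted, describe it as it is.

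2. In the Statistical Analysis section, replace the primary-outcome sentence with: *Time from labor induction to delivery will be compared between arms with a generalized linear model that includes BMI ≥ 40, parity (nulliparous or multiparous) and intended mechanical dilation, as recorded at randomization, as covariates.* The covariate should be intended mechanical dilation. Receipt of a mechanical method, listed under Baseline Characteristics, can be decided after allocation (Design Protocol, At Time of Randomization, item 8).

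3. If enrolment has started on a simple list, keep that list, make change 2, and remove the claim that the scheme achieves balance. Do this before unblinding if possible.

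The cost is two sentences and, if no envelopes have been packed, a different list-generation command. The document does not give enrolment status. All three factors are already known at randomization, and neither the sample size nor any study procedure changes.

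### The primary model should name the three stratification factors as covariates, and the within-stratum allocation as written does not deliver the balance it aims for

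*Combined protocol and SAP*

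**What the plan says.** The Randomization section stratifies on three dichotomous factors: BMI of 40 or more, parity, and "intent to proceed with mechanical dilation at initiation of misoprostol placement". It gives the purpose: "This method will be used to achieve balance among the intervention and control groups". It then says "A separate block will be generated for each combination of covariates", so a block here is one of the eight strata. Within it, "simple randomization will be performed within each block to assign subjects to one of the groups". No block size or other restriction is given.

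The Statistical Analysis section states: "Analysis of the primary outcome will consist of a simple comparison of time from labor induction to delivery between the treatment and control group". The method is generalized linear models, with no covariate, family or link named. The next sentence reads: "Stratified analyses will be used to identify potentially confounding effects". It does not say how the strata would be combined or whether the result would alter the primary estimate.

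The Power Analysis lists "strata = 8, power = 0.85" among its inputs, with means of 15 and 18 h, an SD of 6 h, and about 180 participants at 90 per group.

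The Baseline Characteristics list contains the number of participants who received a mechanical method. The Design Protocol leaves that use to the provider in the steps that follow randomization.

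**The concern.** Stratification can help a trial in two ways. It can balance the factors through restricted allocation, and it can sharpen the estimate when the same factors enter the model. As written, the plan secures neither. Simple randomization within strata puts no restriction on the allocation, and the primary model does not name the factors.

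What is at stake is the width of the confidence interval, and correction of the estimate for chance imbalance in factors the investigators themselves judged important. There is also a prespecification issue: a generalized linear model with no stated covariates leaves the choice to adjust open until the data are seen.

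A smaller risk follows for anyone who adds the factors later. The stratifier is the intention to use mechanical dilation, whereas the baseline table holds the method received. The latter can be decided after randomization and may be affected by the assigned dose, so it cannot stand in for the stratifier.

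**Working it through.** **Inputs from the Power Analysis.** Difference 3 h, SD 6 h, 90 per arm, two-sided alpha 0.05, target power 0.85.

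**The plan's own figure.** The normal formula for two means gives 2 × (1.960 + 1.036)² × 6² / 3² = 71.8, so 72 per arm or 144 in total. An F test with one numerator degree of freedom and f = 0.25 gives 146, still 146 with 8 groups. The stated 180 is not reproduced by a two-arm comparison, but the discrepancy is on the large side and is a separate matter. At 90 per arm the unadjusted power is about 0.92.

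**Allocation.** A fair coin tossed independently for each participant within each stratum is the same process as a fair coin tossed for each participant with no strata. The distribution of imbalance is therefore identical. For a factor with prevalence p, the SD of the between-arm difference is √(2p(1−p)/90). At an assumed p = 0.5 this is √(0.5/90) = 0.0745, or 7.5 percentage points, and the chance of a gap of 10 points or more is about 18%. At assumed prevalences of 35, 20 and 10% that chance is 16, 9 and 3%. Simulation with 180 participants, for a factor at 50% prevalence:

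| Scheme | SD of imbalance (points) | Gap of 10 points or more |
|---|---|---|
| No stratification | 7.5 | 18% |
| Simple randomization in 8 strata | 7.5 | 18% |
| Permuted blocks of 4 in 8 strata | 1.4 | about 0% |

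Arm sizes are not fixed either. Under simple randomization the exact binomial chance that they differ by 20 or more is 15.7%. This barely affects precision: at 100 against 80 the SE is 6 × √(1/100 + 1/80) = 0.90 h, against 0.89 h at 90 per arm.

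**Precision.** R² is the share of outcome variance explained by the three factors. The documents do not give it, so 5 to 30% is an assumed range. The formulas, for a Gaussian model with identity link, are:

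- SE = 6 × √(1−R²) × √(2/90)
- CI half-width = t × SE, with 178 degrees of freedom unadjusted and 175 adjusted (180 − 5)
- power from the noncentral t distribution
- SD of the shift in the unadjusted estimate from chance imbalance = 6 × √R² × √(2/90)

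| Assumed R² | SE (h) | 95% CI half-width (h) | Power for 3 h | SD of shift (h) | Trials with shift above one unadjusted SE |
|---|---|---|---|---|---|
| Unadjusted | 0.89 | 1.77 | 0.92 | – | – |
| 5% | 0.87 | 1.72 | 0.93 | 0.20 | about 0% |
| 10% | 0.85 | 1.67 | 0.94 | 0.28 | 0.2% |
| 20% | 0.80 | 1.58 | 0.96 | 0.40 | 2.5% |
| 30% | 0.75 | 1.48 | 0.98 | 0.49 | 6.8% |

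The SD of the shift is below one unadjusted SE throughout, although single trials can exceed it. The unadjusted interval already allows for this shift; adjustment removes it.

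**Type I error.** This was simulated with 20,000 trials per scheme at an assumed R² of 0.145 (assumed effects 3.4 h for parity, 2.6 h for mechanical dilation, 1.7 h for BMI; assumed prevalences 0.5, 0.5, 0.35). Under simple randomization it was 5.1% unadjusted and 5.0% adjusted. Under blocks of 4 it was 3.3% unadjusted and 4.8% adjusted; with right-skewed residuals these became 3.5% and 5.1%.

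**The case against.** A reader might infer that the factors play no part in the analysis at all. The documents do not support that. A generalized linear model can carry covariates, stratified analyses are mentioned directly after the primary comparison, and the sizing cites eight strata. The authors may well have meant to use them. What can be said is that the primary model names none of them and that the stratified analyses are not linked to its estimate.

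A reader might also infer that the allocation is certainly unrestricted. The section speaks of blocks, a predetermined list and balance, and the Power Analysis expects 90 per group, so loose drafting of a permuted-block list is plausible. That stands as a possibility. But the only block defined is a stratum, and the method named inside it is simple randomization. If permuted blocks are in fact used, the case for adjustment grows, because the unadjusted test becomes conservative.

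The stronger inference, that the primary test is invalid or the trial underpowered, fails: type I error is about 5% under the allocation described, and power exceeds its target. An unadjusted primary comparison is a legitimate choice.

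It is also fair that every gain rests on an assumed R². At 5% the interval half-width shrinks by only 0.04 to 0.05 h, under three minutes. Finally, nothing in the documents proposes the method received as a covariate. The remark on it is a precaution, not an error found in the plan.

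**Conclusion.** The point holds as a loss of precision and a gap in specification. On the text as written, the allocation does not meet its stated aim of balance; this follows exactly from the method named and needs no assumption about prevalence. The primary model does not name the factors on which the trial is stratified.

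The size is modest. Over an assumed R² of 5 to 30%, the SE falls by roughly 3 to 16% and power rises from about 0.92 to between 0.93 and 0.98. Validity and planned power are not in question at the plan's inputs. The adjusted analysis holds its error rate under either allocation scheme. The unadjusted one would run at about 3.5% under permuted blocks, at the assumed R² of 0.145. This should be changed because the improvement is nearly free, not because the trial's conclusion depends on it.

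**What to change.** State in the Statistical Analysis section that the primary generalized linear model includes treatment arm and, as main effects, BMI of 40 or more, parity and intended mechanical dilation, all as recorded at randomization. Make the adjusted mean difference with its 95% CI the primary result and the unadjusted difference a sensitivity analysis. Say explicitly that the covariate is the intention recorded at randomization, not the method received. Give the family and link; if the link is not identity, obtain the mean difference by averaging model predictions over the trial sample.

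In the Randomization section, balance is the stated aim, so replace simple randomization within strata with permuted blocks if the list can still be changed. If it cannot, drop the balance claim. If permuted blocks are already in use, say so and document the block size.

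The model change costs SAP wording and 3 of 178 residual degrees of freedom. It needs no new data, because all three factors must be known to assign the stratum. Permuted blocks would need a new randomization list, which is practical only before enrollment. The model change does not depend on it.

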Ascension Seton Medical Center is a non-profit, private hospital with a level IV maternal care designation that experiences approximately 5000 deliveries a year. Ascension is the primary obstetrical teaching site for the University of Texas at Austin Dell Medical School. The Labor & Delivery ward is a mix of private obstetrical practices and an academic/public teaching component, thus representing a diverse patient population generalizable to the obstetric community as a whole. The academic service is primarily managed by the house staff, midwives, and faculty. This service is comprised of a patient population from the University of Texas at Austin Women's Health Department, CommUnity Care Health Centers, and Ascension Medical Group. The cervical ripening methods employed on labor and delivery consist of a mix of various misoprostol route administrations often times with co-administration of mechanical methods (Cook Balloon) as well. The most commonly employed cervical ripening method involves placement of 25mcg of vaginal misoprostol into the posterior fornix every 4 hours for up to 6 maximum doses. The decision to utilize mechanical ripening, transition to Oxytocin, artificial rupture of membranes, and route of misoprostol administration is at the discretion of the house-staff and faculty on service. However, at this time there does not exist any delineation of cervical ripening methods based on maternal BMI at admission.

Participants:

All patients admitted to Labor & Delivery at Ascension Seton Medical Center will be screened against the inclusion and exclusion criteria by research staff. Eligible patients will be approached by study staff. If interested, the patient will be consented for the study and randomized to either fifty micrograms of vaginal misoprostol dosing (intervention) or twenty-five micrograms of vaginal misoprostol dosing (control) for induction of labor.

Study Criteria:

Inclusion Criteria:

- 1. Singleton gestation
- 2. Age 18 years or older
- 3. Gestational age >= 36 weeks
- 4. BMI \geq 30 kg/m² at time of labor induction
- 5. Cephalic presentation (including successful external cephalic version)
- 6. Cervical dilation <= 3cm
- 7. Intent to proceed with cervical ripening

Exclusion Criteria:

- 1. Contraindication to vaginal delivery (placenta previa, vasa previa, prior classical cesarean, non-vertex presentation, etc.)
- 2. Contraindication to prostaglandin administration (significant allergy, prior cesarean delivery, etc.)

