A Data Safety Monitoring Board (DSMB) will be formed and consist of three individuals: a Maternal Fetal Medicine specialist with expertise in biostatistics ([name]), Obstetrician & Gynecologist ([name]), and Pediatrician/Neonatologist ([name]). These individuals are not involved with the study design nor have potential authorship of the manuscript. The primary purpose of the DSMB will be to monitor patient safety. Additionally, they will have the opportunity to review data collected to monitor the feasibility of the study.

Medication

The patient will be consented for the study and randomized to either fifty micrograms of vaginal misoprostol dosing (intervention) or twenty-five micrograms of vaginal misoprostol dosing (control) for induction of labor. Misoprostol, or Cytotec®, is a synthetic prostaglandin E_1 analog utilized for labor induction purposes and is considered the standard of care in the United States and endorsed by the American College of Obstetrics and Gynecologists¹⁹. A number of different routes and doses exist for misoprostol administration⁶, however 25mcg and 50mcg vaginally are both considered the standard of care for labor induction in the United States.

Consent

Patients who meet inclusion criteria will be identified upon admission to Labor & Delivery at Ascension Seton Medical Center. Study staff will identify qualifying subjects and introduce the study in addition to confirming eligibility. If interested, the patient will be consented for the study by the research nurse or co-investigator. Patients will be randomized to either fifty micrograms of vaginal misoprostol dosing (intervention) or twenty-five micrograms of vaginal misoprostol dosing (control) for induction of labor. If the patient is randomized to the intervention, house staff or a co-investigator will place the vaginal misoprostol per the detailed plan below.

Blinding

Blinding will be achieved by providing misoprostol dosing in prepackaged, numbered envelopes. At randomization, a study number will be assigned and the matching envelope used for misoprostol doses. Misoprostol will be provided as quarters of a whole tablet, using 100 mcg quarters to provide 25 mcg dosing and 200 mcg tablet quarters to provide 50 mcg dosing. When quartered, the 100 and 200 mcg tablets are virtually identical with no distinguishing markings.

Design Protocol

Prior to Randomization

1. Documentation of digital cervical exam prior to randomization.

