- 9. Usual labor and delivery management protocols should be followed by the provider. Usual indications for failure of induction, failure to progress, and second stage arrest should be followed. Although not mandated, it is suggested to providers that women should be allowed at least 18 hours in the latent phase after completion of any ripening, rupture of membranes, and use of oxytocin before considering the induction "failed" and proceeding to cesarean delivery absent any acute maternal or fetal indications.

- 10. Route of delivery and indication for cesarean up to the discretion of the provider.
- 11. Following delivery, universal cord gas collection (arterial, and/or venous) will be collected for all participants
- 12. Postpartum patients will be asked to complete a survey regarding their satisfaction with their cervical ripening method, prior to discharge from the hospital.

Outcomes

Primary Outcomes

1. Interval time from labor induction initiation to delivery (vaginal or cesarean)

Secondary Outcomes

- 1. Interval time from labor induction initiation to complete cervical dilation
- 2. Interval time from labor induction to vaginal delivery
- 3. Vaginal Deliveries
- 4. Cesarean Deliveries
- 5. Indication for Cesarean Delivery (if applicable)
- 6. Operative Deliveries
- 7. Number of Participants exhibiting Uterine Tachysystole (after 4 hours post-misoprostol)
- 8. Number of Participants exhibiting Uterine Tachysystole with Fetal Decelerations
- 9. Number of Participants receiving Terbutaline
- 10. Number of Participants exhibiting Non-Reassuring Fetal Heart Tracings
- 11. Number of Participants diagnosed with Clinical Chorioamnionitis
- 12. Number of Participants diagnosed with Postpartum hemorrhage
- 13. Composite Maternal Morbidity (ICU admission, Sepsis, Need for Transfusion, Death)
- 14. Composite Neonatal Morbidity (ICU admission, APGAR <=7 at 5 minutes, Sepsis, Acidemia identified upon cord collection (pH < 7.15, Base Deficit >12.0 mmol), Induced Hypothermia, Perinatal Death)
- 15. Patient satisfaction of cervical ripening method as measured by the Six Simple Questions and Visual Analog Pain Scale surveys²⁹⁻³⁰.

Baseline Characteristics

- 1. Maternal Age
- 2. Maternal BMI
- 3. Gestational Age
- 4. Parity
- 5. Race
- 6. Admission Cervical Dilation
- 7. Indication for Labor Induction
- 8. Number of Participants receiving a mechanical method of dilation (foley bulb, cook, etc.)
- 9. COVID vaccination status

Outcome Evaluation

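### The primary comparison names no covariate, so it gives up precision that adjusting for cervical dilation recorded before randomization could supply at almost no cost

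*Combined protocol and SAP*

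**What the plan says.** - **Primary analysis (Statistical Analysis):** "Analysis of the primary outcome will consist of a simple comparison of time from labor induction to delivery between the treatment and control group". The sentence goes on to name generalized linear models as the method. It lists no covariate.
- **Other use of covariates (same section):** "Stratified analyses will be used to identify potentially confounding effects". No variable, cut-point or link to the primary estimate is given. The arms are also to be described and tested for comparability, with no stated consequence for the primary model.
- **Measurement of dilation:** the first step under Design Protocol, Prior to Randomization is "Documentation of digital cervical exam prior to randomization". "Admission Cervical Dilation" is item 6 under Baseline Characteristics.
- **Entry range (Inclusion Criteria):** "Cervical dilation <= 3cm", with no lower limit.
- **Randomization:** the stratification factors are "BMI >= 40 kg/m², parity, and intent to proceed with mechanical dilation at initiation of misoprostol placement". Dilation is not among them. Within each combination, "simple randomization will be performed within each block to assign subjects to one of the groups".
- **Design values (Power Analysis):** "3-hour difference (SD=6) between our treatment (M=15 hours) and control (M=18 hours) groups", with 180 women in total and 90 per group.

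**The concern.** The primary outcome times the path from the start of induction to delivery, and dilation at entry is where a woman starts on that path. The plan itself treats dilation as progress: each further dose depends on the cervix still being at 3 cm or less, and the first secondary outcome is time to complete dilation. It is therefore reasonable to expect starting dilation to predict the primary outcome.

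The value will be in hand for every participant before allocation, but neither the allocation nor the primary model uses it. In a linear model, adjusting for such a variable removes the part of the outcome variance it explains and leaves the target, a difference in mean hours, unchanged. Leaving it out gives a wider interval than the same data could support.

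There is also a prespecification side. If the arms turn out to differ in dilation, the plan does not say what follows, so any adjustment would be chosen after the imbalance had been seen.

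**Working it through.** **Inputs.** From Power Analysis: difference 3 h, SD 6 h, 90 per arm, planned power 0.85. From Statistical Analysis: two-sided 5% level. The share of outcome variance explained by dilation, R², is not in the documents; I assume 5–20%, a correlation of about 0.22–0.45.

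**The plan's own figure.** With these inputs a two-arm t-test needs 73 per arm, 146 in total, for 85% power. The stated 180 is not reproduced by a two-arm contrast with one degree of freedom. A numerator with two degrees of freedom gives 178, but the plan does not state that input. This is a separate matter and errs toward a larger trial. What counts here is that 180 women give 91.6% power for 3 h without adjustment.

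**Effect of adjustment.**

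- Standard error: SE = 6 × √(1 − R²) × √(2/90)
- 95% half-width: 1.96 × SE
- Equivalent unadjusted sample size: 180 / (1 − R²)
- Power: two-sided noncentral t, noncentrality = difference / SE

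| Assumed R² | SE (h) | 95% half-width (h) | Power for 3 h | Equivalent N |
|---|---|---|---|---|
| 0 (unadjusted) | 0.894 | 1.75 | 91.6% | 180 |
| 5% | 0.872 | 1.71 | 92.8% | 189 |
| 10% | 0.849 | 1.66 | 94.0% | 200 |
| 20% | 0.800 | 1.57 | 96.2% | 225 |

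The half-width shrinks by 0.04–0.19 h, about 3–11 minutes on each side.

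**If the effect is smaller than planned.** For an assumed true difference of 2 h, the same formulas give 60.4% power unadjusted, 62.6% at R² = 5% and 70.1% at R² = 20%.

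**Chance imbalance.** Imbalance in dilation moves the unadjusted estimate by up to 1.96 × √R² × 6 × √(2/90) at the 95% limit: 0.39 h at R² = 5% and 0.78 h at 20%. This is a component of the unadjusted half-width, not an addition to it:

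- R² = 5%: √(1.709² + 0.392²) = 1.753 h
- R² = 20%: √(1.568² + 0.784²) = 1.753 h

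Both return the unadjusted 1.75 h.

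**Cost if the covariates explain nothing.** With four added terms (dilation and three stratification factors), SE rises by a factor of about √(177/173) = 1.012, or about 1.2%.

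**The case against.** The strongest reply is that nothing is broken. An unadjusted randomized comparison is unbiased and holds its type I error. Power under the plan's own inputs is already above the 85% sought. The gain rests entirely on an R² that no document supplies. Entry at 3 cm or less, together with the exclusion of women not intended for ripening (a favorable Bishop score is one example given), narrows the range of dilation and may keep R² low. At a correlation of 0.2 the gain in power for 3 h is about one percentage point. All of this stands, and it limits the point to one of efficiency.

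Two stronger readings are tempting:

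- A reader might infer that chance imbalance in dilation is a further error on top of the wide interval, or that it biases the result. The decomposition above shows otherwise: the unadjusted interval already contains that component on average.
- A reader might infer that the plan takes no account of baseline factors. It does foresee stratified analyses, and generalized linear models can accommodate covariates. But those analyses name no variable and leave the primary estimate as it is, so they do not recover the lost precision.

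What the reply does not answer is why a baseline value already collected should go unused when adding it costs so little.

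**Conclusion.** The point holds as a loss of precision, not of validity. Under the plan's SD of 6 h and 90 per arm, adjusting for dilation would cut the standard error by about 2.5–10.6% (0.894 h to 0.872–0.800 h), equivalent to 9–45 additional women. The range depends on the assumed 5–20% of variance explained and on a roughly linear relation between dilation and hours to delivery; the lower end is quite possible given the restricted entry range. If the true effect is 3 h and the SD is 6 h, the trial is adequately powered either way. The gain matters more if the effect is smaller or the spread larger. Neither is remote, because the design values come from a trial of a different comparison: Foley bulb plus vaginal misoprostol against vaginal misoprostol alone. The change is worth making because it is nearly free and settles the adjustment question before the data are seen.

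**What to change.** In Statistical Analysis, before unblinding, replace the simple comparison with a prespecified primary generalized linear model: hours from induction start to delivery on arm, admission cervical dilation (cm, continuous, from the exam documented before randomization), and the three stratification factors (BMI ≥ 40 kg/m², parity, intended mechanical dilation). State that the covariate list is fixed. Report the arm difference in hours with a 95% confidence interval, and keep the unadjusted comparison as a sensitivity analysis.

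The change is a sentence or two of text. It needs no new data, visits or participants and uses four degrees of freedom. If the covariates explained nothing, the loss of precision would be about 1–2% or less.
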